6.3 Longitudinal assessments

Day 1 for the short-term double-blind treatment period is the start date of double-blind treatment medication. The observation closest to the target day (and time where applicable) is the measurement used in the analysis for each scheduled visit.

The following visit window will apply for all laboratory parameters, vital signs and physical measurements in the short-term double-blind treatment period up to 24 weeks.

Table 9 Visit Windows for Short-term Double-blind Treatment Period Up to Week 24

Visit	Target Day	Day Range
Week 1	8	Post-baseline -11*
Week 2	15	12-22*
Week 4	29	23-43*
Week 8	57	44-71*
Week 12	85	72-106*
Week 18	127	107-148*

Table 9 Visit Windows for Short-term Double-blind Treatment Period Up to Week 24

Visit	Target Day	Day Range
Week 24	169	149 - Last day of double-blind treatment + 8 day for HbA1c, body weight, BMI, patient reported outcomes or 149 - Last day of double-blind treatment +1 day for insulin dose, CGM parameters, FPG, SMBG

* on or before the last day of double-blind treatment.

Table 10 Visit Windows for Short-term Double-blind Treatment Period Up to Week 24 for CGM parameters, Total daily Insulin and 6-point SMBG

Visit	Target Day	Day Range
Week 2	15	1-40*
Week 12	85	60-110*
Week 24	169	140- Last day of double-blind treatment

* on or before the last day of double-blind treatment.

The use of post double-blind treatment observations is specified in Section 6.4.

For all safety laboratory parameters, the use of post-double-blind treatment observations is specified in Section 4.2.4.5.

For laboratory and non-laboratory parameters, if a subject has more than one measurement included within a window, the assessment closest to the target day will be used. In case of ties between observations located on different sides of the target day, the earlier assessment will be used. In case of ties located on the same side of the target day (i.e. more than one value for the same day but different time), the value with the earlier entry date/time will be used.

For measurements referring to 24-hour collection periods (i.e. daily insulin dose) and those referring to multiple data collection points over multiple days (i.e. 6-point measurement parameters and CGM parameters) more than one value will be included in the analysis window. The value for analysis for the visit window will be calculated as the daily average of all available values for analysis for each parameter falling in the analysis window.

For the shift tables for nominal ECG parameter of normal/abnormal the following rules apply. If more than one ECG measurement is performed within a specified time window, an abnormal ECG value will be chosen over a normal ECG value. If more than two abnormal or

two normal ECG values are within the same time window, the one closest to the target date will be used.

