4.2.3.1 Primary efficacy analysis

The primary endpoint is the change in HbA1c from baseline to Week 24. The comparison between each dapagliflozin group and placebo are of interest for this study.

The primary endpoint is the change in HbA1c from baseline to Week 24. The primary estimand for the treatment difference at Week 24 if subjects did not discontinue randomized treatment. The primary analysis of the change in HbA1c from baseline to Week 24 will be based on a longitudinal repeated measures analysis using 'direct likelihood' (see Section 4.1.6.1). The analysis will include all available data up to Week 24 or until premature discontinuation of randomized treatment, whichever occurs first. The analysis will be conducted regardless of insulin up-titration.

The model will use subjects in the primary efficacy dataset (i.e., Full Analysis Set) who have a baseline assessment and any post-baseline double-blind treatment period assessment.

For subjects whose post-randomization insulin dose is up-titrated by more than 25% of insulin relative to baseline, measurements obtained after the first instance the 25% up-titration criteria

is met will correspond to rescue and be included in the primary analysis but excluded in one of sensitivity analyses.

Point estimates and 95% confidence intervals for the mean change within each treatment group as well as the difference in mean change between each dapagliflozin treatment group and placebo will be calculated. Student t-statistics corresponding to the Type III sums of squares for the differences in the least squares means between each dapagliflozin group and placebo at Week 24 will be calculated.

To assess the robustness of the primary efficacy analysis for the change in HbA1c from baseline to Week 24, additional sensitivity analyses will be carried out using the following approaches:

- A longitudinal repeated measures analysis, similar to the primary analysis, excluding measurements obtained after the first instance the 25% up-titration criteria is met.
- ANCOVA analysis including subjects in the Full Analysis Set who have a baseline assessment and at least one post-baseline assessment using LOCF methodology for Week 24 (see Section 4.1.5.1).
- ANCOVA analysis including subjects in the Full Analysis Set who have a baseline assessment and a Week 24 assessment (i.e. a “completers” analysis, but without LOCF methodology) (see Section 4.1.5.1).

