- A longitudinal repeated measures analysis, similar to the primary analysis, but including subjects in the Per Protocol Analysis Set who have a baseline assessment and any post-baseline assessment. This analysis will be performed only if > 10% of the subjects in any treatment group in the Full Analysis Set have exclusion of the primary efficacy variable data which may have been affected by protocol deviations.
- The ITT estimand, i.e., treatment difference at Week 24 regardless of treatment discontinuation, will be evaluated as the secondary estimand of the primary endpoint, using a longitudinal repeated measures analysis using ‘direct likelihood’ (see Section 4.1.6.1). The analysis of the ITT estimand will include all available data up to Week 24, regardless of insulin up-titration and regardless of premature discontinuation of randomized treatment.
- A de facto ITT estimand, i.e. treatment difference at Week 24 regardless of whether treatment was actually taken, will be evaluated as another estimand of the primary endpoint. This analysis will include all randomized subjects and all available HbA1c measurements, regardless of treatment adherence. For the subjects who discontinue treatment early and do not have HbA1c measurements at Week 24, their Week 24 HbA1c values will be imputed based on the data from those retrieved subjects in the same treatment group, i.e. those who discontinue treatment early but have HbA1c measurements at Week 24, using a multiple imputation approach. If the number of retrieved subjects is insufficient to inform the imputation, the missing data will instead be imputed based on placebo data only, using a multiple imputation approach. The change from baseline to Week 24 in HbA1c will be analyzed using an ANCOVA model with factors of treatment group and randomization stratification factor (i.e. 1 term for each combination of all stratification factors) and covariate for baseline HbA1c.

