6.4 Post-treatment observations

While short-term double-blind treatment period (up to the start of long-term treatment period) efficacy observations will be listed regardless of whether the subject was taking blinded study drug, observations may not contribute to summaries/analyses if they are measured after the last dose of short-term double-blind study medication (up to the start of long-term treatment period) as indicated below: HbA1c, body weight, BMI, patient reported outcomes, will be summarized/analyzed only if measured on or prior to the 8th day after the last double-blind drug treatment date. Please note that the analysis of the ITT estimand for HbA1c will include all available HbA1c data up to Week 24, regardless of premature discontinuation of randomized treatment.

Insulin dose, CGM parameters, FPG, SMBG will be summarized only if measured on or prior to the first day after the last double-blind drug treatment date.

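### HbA1c visit windows tied to the last dose leave no window for the off-treatment Week 24 values that the ITT and de facto analyses need, and other post-dose rules disagree

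*SAP*

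**What the plan says.** **Assigning a value to a week.** SAP Section 4.1.2.2 leaves this entirely to the conventions of Section 6.3. Table 9 there covers all laboratory parameters. Its rows from Week 1 to Week 18 carry an asterisk restricting them to values "on or before the last day of double-blind treatment". The Week 24 row reads "149 - Last day of double-blind treatment + 8 day for HbA1c, body weight, BMI, patient reported outcomes".

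**Post-treatment values.** Section 6.4 says HbA1c "will be summarized/analyzed only if measured on or prior to the 8th day after the last double-blind drug treatment date". It names no visit. It then notes that the ITT analysis of HbA1c uses everything up to Week 24, whether or not treatment was stopped early. Section 6.3 refers to Section 6.4 for the use of post-treatment observations.

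**Estimands.** Section 4.2.3.1 runs the primary analysis up to Week 24 or "until premature discontinuation of randomized treatment, whichever occurs first". For the secondary estimand it says: "The analysis of the ITT estimand will include all available data up to Week 24, regardless of insulin up-titration and regardless of premature discontinuation". The de facto ITT analysis also takes all HbA1c irrespective of adherence. It imputes missing Week 24 values from retrieved subjects in the same arm, meaning those who stopped early but have a Week 24 HbA1c. If there are too few of them, it imputes from placebo data only.

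**Insulin, CGM and SMBG.** Table 9 gives Week 24 as "149 - Last day of double-blind treatment +1 day for insulin dose, CGM parameters, FPG, SMBG". Table 10, which is specific to insulin, CGM and SMBG, gives "140- Last day of double-blind treatment". Section 6.4 allows these measures up to one day after the last dose.

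**The concern.** A visit window should say which scheduled visit a value represents. Whether a value counts for a given estimand is a separate question. Table 9 merges the two by building the last dose into every window. That can work for an on-treatment estimand. It cannot work for the two estimands that use data after treatment has stopped, because the same table is the only rule for labelling those data.

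The consequence is sharpest for the de facto analysis. Its imputation donors are defined by having a Week 24 HbA1c after stopping early. If the window rule denies that label, the donor pool shrinks or disappears, and the choice between same-arm and placebo-based imputation is settled by a table footnote.

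For the primary analysis, three sections give different answers on whether an HbA1c drawn a few days after an early last dose is used. Two programmers could build different primary datasets from the same text. For insulin and CGM, values are averaged over the window, so its limits are part of the endpoint definition. Insulin dose and three CGM measures make up four of the six ordered secondary endpoints.

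**Working it through.** Let L be the day of the last dose and d the day of the HbA1c draw.

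**1. The plan's own limits.** The limits in Table 9 are midpoints between target days: (8+15)/2 = 11.5, (15+29)/2 = 22, (29+57)/2 = 43, (57+85)/2 = 71, (85+127)/2 = 106, (127+169)/2 = 148. These reproduce the printed upper limits 11, 22, 43, 71, 106 and 148, and Week 24 starts at 149. The calendar part of the table is sound; the last-dose conditions cause the difficulty.

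**2. Week 24 window for HbA1c: 149 ≤ d ≤ L + 8.**
- It is non-empty only if L + 8 ≥ 149, so L ≥ 141.
- It contains Day 169 only if L + 8 ≥ 169, so L ≥ 161.
- Example: for L = 60 the window runs from 149 to 68 and is empty. HbA1c on Days 85, 127 and 169 falls in no window, because the asterisk bars the first two and the empty range bars the third.
- Any value that does fall in the window was drawn at most 8 days after the last dose.

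On a literal reading, nobody who stops before Day 141 can be a retrieved donor. Someone who stops between Day 141 and Day 160 can be one only with a draw before Day 169. Every donor would have been off drug for 8 days or less when sampled.

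**3. HbA1c 1 to 8 days after an early last dose.** Take L = 80 and d = 83.

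| Rule | Condition | Result |
|---|---|---|
| Section 6.4 | 83 ≤ 80 + 8 = 88 | not barred |
| Table 9, Week 12 (72–106*) | 83 ≤ 80 is false | barred |
| Section 4.2.3.1, primary analysis | data end at discontinuation, no grace days stated | out |

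Over L = 1 to 168 and 1 to 8 days after the last dose there are 168 × 8 = 1344 combinations. For L ≤ 140 all eight days have no Table 9 window: 140 × 8 = 1120. For L = 141 to 147 the unassigned days number 7, 6, 5, 4, 3, 2 and 1, which sum to 28. From L = 148 there are none. The total is 1120 + 28 = 1148 of 1344. This counts calendar combinations, not subjects.

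Applying +8 days in every row would reduce 1148 to 0. It would not repair step 2, because Day 169 would still have no window for L < 161.

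**4. Insulin, CGM and SMBG at Week 24.** Table 9 gives Day 149 to L + 1, Table 10 gives Day 140 to L, and Section 6.4 gives a ceiling of L + 1. Days 140 to 148 are in under Table 10 and out under Table 9. The day after the last dose is in under Table 9 and out under Table 10. For L = 145, Table 10 gives Days 140 to 145, while Table 9 gives 149 to 146, which is empty.

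**5. Number of subjects.** The SAP states no rate of early treatment discontinuation. The 5% in Section 1.3 is for subjects with no post-baseline assessment. If 5% to 15% of 256 per arm stopped early (an assumption), that would be 0.05 × 256 ≈ 13 to 0.15 × 256 ≈ 38 subjects per arm. This is a ceiling for steps 2 and 3, since each also requires a draw at the relevant time.

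**The case against.** The strongest reply is that the SAP already settles most of this. Section 6.3 defers to Section 6.4 for post-treatment observations. Section 6.4 and Section 4.2.3.1 both say that ITT HbA1c is used regardless of discontinuation, and a sensible programmer would let that specific exception override the table. Section 6.4 also says "only if measured on or prior to the 8th day after the last double-blind drug treatment date", which is a ceiling and does not promise inclusion. A draw 3 days after an early last dose is therefore not positively admitted there. Table 10 is headed for exactly the parameters in dispute. CGM is scheduled from Week 22 (Day 22 × 7 + 1 = 155), so a lower limit of 140 or 149 captures the same scheduled data in completers.

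Much of this stands: the intent for the ITT estimand is clear, and the insulin, CGM and SMBG mismatch is minor for completers on schedule. But the deferral does not lift the asterisk or the Week 24 upper limit. The exception says the data are used without saying which week they belong to, and Week 24 has no calendar upper day once the last-dose limit is removed. The exception also does not name the de facto estimand.

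A reader might infer more, and the documents do not support it:
- **That all retrieved Week 24 values will be lost.** This requires applying the table against the stated exception.
- **That 13 to 38 subjects per arm lose their last HbA1c.** This requires every early stopper to be sampled 1 to 8 days after the last dose. A draw on the last dose day is unaffected, and one after day +8 is excluded under both Section 6.4 and Table 9.
- **That early stoppers get no allowance at all.** Those stopping on Days 141 to 147 get part of it, and those from Day 148 all of it.
- **That this undermines the missing-at-random assumption.** Nothing in the SAP quantifies how much these last values contribute.

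**Conclusion.** The point holds as an inconsistency between stated rules. The main defect is that the SAP's only week-assignment rule gives no Week 24 window to off-treatment HbA1c from anyone whose last dose is before Day 141, and excludes Day 169 for any last dose before Day 161. Two of the plan's own estimands require those values. For the de facto estimand, the wording as it stands pushes toward the placebo-based fallback, and its exemption is not stated in Section 6.4.

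The disagreement over HbA1c 1 to 8 days after an early last dose is real but of unknown size. It depends on when termination samples are drawn, which the SAP does not state, and it may affect few subjects or none. Its effect on LOCF analyses also depends on reading, since Section 4.1.2.5 does not clearly require a windowed value. The Table 9 and Table 10 conflict is real and mainly concerns subjects who stop near Week 24.

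The day thresholds follow from the printed limits alone and need no assumption. Only the 5% to 15% range is assumed. The sample size is unaffected.

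**What to change.** 1. **ITT and de facto analyses.** Use calendar-day windows with no last-dose cut-off for HbA1c. State a calendar upper day for Week 24. A range symmetric about the target would end on Day 189 (169 − 149 = 20; 169 + 20 = 189), but the sponsor may choose another day. Name the de facto estimand beside the ITT estimand in the Section 6.4 exception.
2. **Primary estimand.** State one last-dose cut-off, apply it in every window, and make the Table 9 footnote, Section 6.4 and Section 4.2.3.1 agree. Using the 8 days of Section 6.4 throughout is one consistent option. Allowing no grace days is another, and the choice is the sponsor's. Say whether LOCF uses the same cut-off.
3. **Insulin, CGM and SMBG.** Remove them from the Week 24 row of Table 9, leaving FPG there. Keep one Week 24 range in Table 10 that agrees with Section 6.4.

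The cost is SAP wording and a change to the windowing program. No new data are needed. The change should be made before unblinding.

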6.4 Post-treatment observations

While short-term double-blind treatment period (up to the start of long-term treatment period) efficacy observations will be listed regardless of whether the subject was taking blinded study drug, observations may not contribute to summaries/analyses if they are measured after the last dose of short-term double-blind study medication (up to the start of long-term treatment period) as indicated below: HbA1c, body weight, BMI, patient reported outcomes, will be summarized/analyzed only if measured on or prior to the 8th day after the last double-blind drug treatment date. Please note that the analysis of the ITT estimand for HbA1c will include all available HbA1c data up to Week 24, regardless of premature discontinuation of randomized treatment.

Insulin dose, CGM parameters, FPG, SMBG will be summarized only if measured on or prior to the first day after the last double-blind drug treatment date.

6.5 Assignment of doses to adverse events and laboratory assessments

In case of missing dates and/or times, prior to assigning the treatment that the subject received at the onset of an AE or at the time of a laboratory assessment, imputation rules will be applied as follows:

For AEs, a missing or incomplete onset date will be imputed according to the following conventions:

- If the onset date for an AE is missing or incomplete, an imputed date will be derived to slot the event to an appropriate analysis period. This derived date will not be reported in summary tables or listings. Every effort will be made to determine the actual onset date for the event or to obtain a reliable estimate for the onset date from the investigator.
- If an onset date is missing, the derived onset date will be calculated as the first non-missing valid date from the following list (in order of precedence):
 - First active study medication date
 - Consent date
 - Visit date corresponding to the visit at which the event was reported.
 - If a valid non-missing date is not available for any of these dates, the derived onset date will be set to missing.
- If an onset date is incomplete, the derived onset date will be calculated using the following algorithm:
 - Calculate a surrogate date as the first non-missing valid date from the following list (in order of precedence):
 - ◆ First active study medication date
 - ◆ Consent date
 - ◆ Visit date corresponding to the visit at which the event was reported

- ◆ If a valid non-missing date is not available for any of these dates, the surrogate date will be set to missing.
- Based on the information provided, set the derived date to the earliest possible date. If only a year is provided, set the derived date to January first of that year. If a year and month is provided, set the derived date to the first day of that month.
- If the surrogate date is non-missing then:
 - ◆ If the derived date is on or after the surrogate date use the derived date as calculated
 - ◆ If the derived date is prior to the surrogate date and the surrogate date is consistent with the partial data provided for the onset date, use the surrogate date as the derived date
 - ◆ If the derived date is prior to the surrogate date and the surrogate date is not consistent with the partial data provided for the onset date then set the derived onset date to be the latest possible date based on the partial onset date information provided. If only a year is provided, set the derived date to December 31st of that year. If a year and month is provided, set the derived date to the last day of that month.
- If all three dates used to determine the surrogate date are missing, then based on the information provided, set the derived date to the earliest possible date. If only a year is provided, set the derived date to January first of that year. If a year and month is provided, set the derived date to the first day of that month.

A drug treatment file will be created, containing any starting and stopping dose as well as intermediate dose changes within each study period, with dates and times as recorded on the CRF. In this context,

- Unless otherwise specified in study-specific SAP, the date of the first dose of study medication is defined as the earliest start date with number of tablets > 0 reported on the study medication page.
- the date of the last dose of study medication is defined as the latest start or stop date with number of tablets > 0 reported on the study medication page.
- if a dosing time is missing for a starting dose of study drug in a study period or a dose change, then it is defaulted to 9:00 if there are AM and BID dosing in the study, and it is defaulted to 19:00 if there is only PM dosing in the study.
- if there's a gap in the dosing information, then the dosing time corresponding to the start date of the gap, is defaulted to 00:00.

If a dosing time is missing for a last stop dosing date for the study drug in a study period, then it is defaulted to 23:59 when there is no study medication in the next study period, or is defaulted to 1 minute before the starting dose time of the study medication in the next study period when available.

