4.2.4.1 Adverse events

Adverse Events (AEs) will be classified by Primary System Organ Class (SOC) and Preferred Term (PT) according to the Medical Dictionary for Regulatory Activities (MedDRA). Summaries of AEs will use the version of MedDRA that is current at the time of database lock.

No statistical test will be performed to compare adverse event rates between treatment groups. This policy was adopted to recognize the lack of power and the potential for misleading

interpretation based on repeated statistical tests which increase the family wise Type I error level.

Counting rules for adverse events are described in Section 6.7.

In summaries by SOC and PT, AEs will be sorted by decreasing frequency within each SOC and PT according to the highest Dapagliflozin dose group. In summaries by PT, AEs will be sorted by decreasing frequency within PT according to the highest dapagliflozin dose group.

Separate pages to capture events of hypoglycemia are contained within the CRF.

Hypoglycemia or discontinuation due to hypoglycemia would not be reported on an AE CRF page unless the event fulfilled criteria for a Serious AE (SAE) in which case an SAE form would be completed. Hypoglycemia events that are reported as SAEs will be included in all summaries of AEs or SAEs (see Section All Adverse Events). Separate summaries will be provided including hypoglycemia events reported on that special CRF pages (see Section Hypoglycemia).

All Adverse Events

All adverse events (serious and non-serious, excluding hypoglycemic and DKA events that are not reported as SAEs) with onset during the short-term double-blind treatment period will be summarized by SOC, PT, and treatment group, for both the primary and sensitivity safety analyses. In addition, a subject listing of all reported adverse events will be produced, displaying all events (including pre-treatment events) that occurred prior to the start date of long-term treatment period. All adverse events (serious and non-serious) including all hypoglycemic events will also be summarized by treatment group.

AEs and SAEs with an onset from Day 1 of the short-term double-blind treatment period up to and including 4 days and 30 days respectively, after the last dose date in the short-term double-blind treatment period (or up to the start date of the long-term treatment period, whichever comes first) will be considered as occurring during the short-term double-blind treatment period.

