A DKA Adjudication Committee, blinded to the treatment of the subjects, will independently adjudicate all the DKA events reported by the investigators and those identified based on pre-defined algorithm during the study period. A separate Adjudication Manual will define and describe the procedure for the handling, reporting, and classification of these cases.

DKA events with an onset from Day 1 of the lead-in period up to and including 1 day prior to start of short-term double blind treatment period will be considered as occurring during lead-in period, whereas DKA events with an onset from Day 1 of the short-term double-blind treatment period up to and including 4 days after the last dose date in the short-term double-blind treatment period (or up to the start date of the long-term treatment period, whichever comes first) will be considered as occurring during the short-term double-blind treatment period. The proportion of subjects with DKA events will be tabulated by treatment group in the lead-in period and the short-term double-blind treatment period.

SAEs of DKA with an onset during the short-term double-blind treatment period and leading to discontinuation of study medication will be summarized by treatment group. When summarizing DKA events leading to discontinuation, no upper cutoff day windows are applied.

The number and percentage of subjects with DKA events will be summarized by frequency of events per subject (recurrence; 1, 2, 3, > 3). The total number of events by treatment group will be summarized for the lead in period and the short-term double-blind treatment period.

The exposure adjusted incidence rate of definite DKA events (including recurrences) will be summarized by monthly intervals in order to assess any over time changes in the incidence rate.

Time to first DKA event will be presented by treatment group using a Kaplan-Meier curve using methodology described in Section 4.1.7. A plot will be presented only when there are at least 5 events in one treatment group. An accompanying table of the cumulative proportion of subjects with time to first DKA event at specific time points during the short-term double-blind treatment period will be produced.

A listing of subjects will be produced and it will display all confirmed adjudicated DKA events with an onset date/time from the start date/time of double-blind treatment period up to the start date of the long-term treatment period.

Hypoglycemia

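### Section 6.5 can date an adverse event to first dose even when its own stop date or reporting visit shows that it came earlier

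*SAP*

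**What the plan says.** Section 6.5 states the purpose of the rule: "an imputed date will be derived to slot the event to an appropriate analysis period".

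- **Onset completely missing.** "If an onset date is missing, the derived onset date will be calculated as the first non-missing valid date from the following list". The list is, in order, "First active study medication date", the consent date, and "Visit date corresponding to the visit at which the event was reported".
- **Onset incomplete.** The same list supplies a surrogate date, and the derived date starts as the earliest date compatible with what was recorded. If that is on or after the surrogate, it stands. If it is earlier, and "the surrogate date is consistent with the partial data provided for the onset date, use the surrogate date as the derived date". If it is earlier and the surrogate does not fit the partial date, the rule is to "set the derived onset date to be the latest possible date based on the partial onset date information provided".

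Section 6.5 also promises every effort to obtain the true onset date or a reliable estimate from the investigator.

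The derived date matters because Section 4.2.4.1 counts "AEs and SAEs with an onset from Day 1 of the short-term double-blind treatment period up to and including 4 days and 30 days" after the last dose (for AEs and SAEs respectively) as belonging to the short-term period. Section 4.2.4.4 uses the same window for events of special interest unless it says otherwise. Section 6.3 defines Day 1 as the start date of double-blind medication. The listings in Section 4.2.4.1 include pre-treatment events, so such events are expected in the database.

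**The concern.** Placing an event of unknown onset in the treatment period is a reasonable default when nothing else is known. Here something else is often known. Section 4.2.4.1 uses onset and resolution dates to separate new occurrences from continuing ones, so resolution dates are in the data. Section 6.5 itself names the reporting visit. Yet no branch reads the stop date, and the visit can be reached only if both the first-dose date and the consent date are missing, which does not happen for a subject with a recorded first dose.

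The rule can therefore override the subject's own record. It can produce an onset later than the recorded end or later than the visit that reported the event, and put a pre-treatment event in the on-treatment tables. At stake is the correctness of the 24-week AE summaries and, for genital and urinary-tract infection, of the first point on the Kaplan-Meier curves.

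**Working it through.** The SAP states no figure to reproduce. The check applies the Section 6.5 rule literally, taking active study medication to mean the double-blind tablets in every arm.

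**Worked cases.** Illustrative inputs: first dose 20 March 2016, consent 10 January 2016, reporting visit 12 March 2016. The surrogate is 20 March 2016 in every case.

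1. Onset missing, ended 10 February. Derived onset 20 March, on-treatment. The record shows pre-treatment.
2. Onset March 2016, ended 10 March. The earliest possible date, 1 March, is before 20 March, and 20 March lies in March. Derived onset 20 March, on-treatment, 20 − 10 = 10 days after the event ended.
3. Onset 2016 only, ended 10 February. The earliest possible date is 1 January, and 20 March lies in 2016. Derived onset 20 March, on-treatment. The record shows pre-treatment.
4. Onset February 2016, ended 25 February. 20 March is not in February, so the derived onset is 29 February. That is after the recorded end, but the period is right: pre-treatment.
5. Onset 2015 only. Derived onset 31 December 2015, pre-treatment, right.

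The fault is thus confined to completely missing onsets and to partial onsets whose month or year contains the first dose.

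**With the cap.** Derived onset = min(Section 6.5 date, stop date, reporting visit):

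- Case 1: min(20 March, 10 February, 12 March) = 10 February.
- Case 2: min(20 March, 10 March, 12 March) = 10 March.
- Case 3: min(20 March, 10 February, 12 March) = 10 February.

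All three return to pre-treatment.

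**How often the rule moves a lead-in event to Day 1.** Input: a lead-in of L = 56 ± 5 days (notes to the study schematic in Section 1.2). Assumptions: first doses spread evenly over the 365 days of a non-leap year, and true onsets spread evenly over the L days before first dose. This gives 365 × L pairs of dates.

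- *Month and year recorded.* A first dose on day d of a month has d − 1 earlier days in that month. A month of n days contributes n(n − 1)/2. The sum is 7 × 465 + 4 × 435 + 378 = 5,373. Shares: L = 51, 5,373/18,615 = 28.9%; L = 56, 5,373/20,440 = 26.3%; L = 61, 5,373/22,265 = 24.1%.
- *Year only.* Pairs falling in the previous year number L(L + 1)/2. Shares: L = 51, (18,615 − 1,326)/18,615 = 92.9%; L = 56, (20,440 − 1,596)/20,440 = 92.2%; L = 61, (22,265 − 1,891)/22,265 = 91.5%.
- *Completely missing.* 100%.

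These are shares of incompletely dated lead-in events that the rule moves to Day 1. They are not shares proved wrong: they include events still ongoing at first dose and events first reported at the Day 1 visit, for which neither date contradicts a Day 1 onset. The provably wrong share is smaller and cannot be computed from the SAP.

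**The case against.** The best defence is that the rule is conservative: it over-counts on-treatment events rather than hiding them, it applies only after every effort to obtain the true date, and it leaves partial dates from an earlier month or year in the pre-treatment period. All of that is so. It justifies the default when the record is silent, but not a derived date that the record contradicts. The promise to query sites reduces the number of imputed dates without bounding those that remain. The sponsor's standard algorithms cited in Section 4.2.4.1 are not shown; as described there, they separate new from continuing occurrences and do not limit the derived onset. The SAP does bound an imputed date elsewhere: in Section 6.1 an imputed diagnosis date after consent is reset to consent.

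A reader might infer more than the SAP supports:

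- **Material dilution of arm differences.** If a fraction q of subjects in each arm gains a spurious event independently, a difference in incidence is multiplied by (1 − q). For an assumed difference of 5.0 points, q = 0.5% gives 5.0 × 0.995 = 4.975, and q = 2% gives 5.0 × 0.98 = 4.9. Section 4.2.4.1 also plans no tests of AE rates.
- **A distorted split of diabetic ketoacidosis.** Section 4.2.4.4 does assign "DKA events with an onset from Day 1 of the lead-in period up to and including 1 day prior to start of short-term" treatment to the lead-in, but these events go to a blinded adjudication committee, and nothing suggests that they would lack an onset date.
- **Different handling of placebo.** If active excluded placebo, a missing onset on placebo would fall back to consent. The SAP does not require that reading: Section 6.5 defines first dose by tablets of study medication, and Section 6.9 counts dapagliflozin and placebo subjects' tablets alike. One clarifying word would still help.
- **Events first reported in the long-term period.** A missing onset there is also set to Day 1, but the true onset may lie within the 24 weeks. Removing such events from some analyses is a judgement call and could make the tables disagree.

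**Conclusion.** The point holds in a limited form. For a completely missing onset, or a partial onset whose month or year contains the first dose, Section 6.5 assigns first dose without checking the two dates that could rule it out. When either does so, the analysis period is wrong, and the derived onset may fall after the event's end.

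This is a minor-to-moderate matter for the safety summaries. The number of affected events is not given and is probably small. The 24–29%, 92% and 100% shares rest on evenly spread onsets and describe how far the rule reaches, not how often it errs. The arms are handled alike provided that active means double-blind study medication. Efficacy analyses are unaffected.

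**What to change.** Add to Section 6.5, before the analysis period is assigned:

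- The derived onset may not be later than the earlier of (a) the AE stop date, or its latest possible value if the stop date is partial, and (b) the date of the visit at which the event was first reported.
- The first-dose date is imputed only when both dates are compatible with an onset on or after first dose.
- The first active study medication date means the first dose of double-blind medication in any arm.

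An event with no stop date is then governed by the reporting visit alone. An event first reported on the first-dose date, with no earlier stop date, stays on Day 1.

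The cost is a short SAP edit and a few lines in the date-derivation program, using dates that the SAP already refers to. The downside is slightly fewer events counted as on-treatment, each shown by its own record to precede first dose. The change can be made before unblinding.
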